**Confidential Information**

The information contained in this document is confidential and the information contained within it may not be reproduced or otherwise disseminated without the approval of Eli Lilly and Company or its subsidiaries.

**Note to Regulatory Authorities:** this document may contain protected personal data and/or commercially confidential information exempt from public disclosure. Eli Lilly and Company requests consultation regarding release/redaction prior to any public release. In the United States, this document is subject to Freedom of Information Act (FOIA) Exemption 4 and may not be reproduced or otherwise disseminated without the written approval of Eli Lilly and Company or its subsidiaries..

Dulaglutide (LY2189265)

Study H9X-MC-GBGE is a Phase 3b, randomized, double-blind, placebo-controlled trial that investigates the effect of the addition of once-weekly dulaglutide 1.5 mg or 0.75 mg to SGLT2 inhibitors, with or without concomitant use of metformin, on change from baseline in hemoglobin A1c (HbA1c) at 24 weeks in patients with type 2 diabetes mellitus.

Eli Lilly and Company  
Indianapolis, Indiana USA 46285  
Protocol H9X-MC-GBGE  
Phase 3b

Statistical Analysis Plan Version 1.0 electronically signed and approved by Lilly: 19 November 2015.

Statistical Analysis Plan Version 2 electronically signed and approved by Lilly on date provided below.

Approval Date: 01-Apr-2016 GMT

Redacted Version

### 3. Revision History

The protocol for this study was approved on 29-Jul-2015. Protocol amendment (a) was approved on 21-Aug-2015. Version 1 of this Statistical Analysis Plan (SAP) was approved prior to first patient visit (FPV). Version 2 of the SAP was developed based on the request from FDA that the ITT estimand (treatment regimen estimand, including the post-rescuedata) be used for the primary analysis. This revision was approved before the last patient visit. The following changes were made in this revision: 1) sample size due to protocol amendment; 2) the definition of the completers population for consistency with other dulaglutide studies; 3) hypoglycemia rate analysis using linear mixed model instead of GEE for better control of the type I error rate; 4) including baseline HbA1c-by-visit interaction term in the HbA1c target analysis to improve model convergence.

## 4. Study Objectives

Table GBGE.4.1 shows the objectives and endpoints of the study.

**Table GBGE.4.1. Objectives and Endpoints**

Objectives	Endpoints

Primary To demonstrate that once-weekly dulaglutide (1.5 mg and/or 0.75 mg) is superior to placebo as measured by HbA1c at 24 weeks (change from baseline) in patients with inadequately controlled T2D on concomitant SGLT2 inhibitor therapy.
	
 
• The change in HbA1c from baseline to 24 weeks
 

Secondary Key secondary efficacy objectives (controlled for type 1 error) are to compare dulaglutide 1.5 mg and 0.75 mg to placebo at 24 weeks
 
Other secondary efficacy objectives are to compare dulaglutide 1.5 mg and 0.75 mg to placebo at 24 weeks
 
Secondary safety objectives are to compare dulaglutide 1.5 mg and 0.75 mg to placebo at 24 weeks
	
 
• Proportion of patients with HbA1c target values of <7.0% at 24 weeks
 
• The change in FBG (central laboratory) from baseline to 24 weeks
 
• The change in body weight from baseline to 24 weeks
 
 
 
• Proportion of patients with HbA1c target values of ≤6.5% at 24 weeks
 
• The change in 6-point SMPG profile from baseline to 24 weeks
 
• The change in fasting glucagon from baseline to 24 weeks
 
 
Incidence of:
 
 
• Treatment-emergent adverse events (TEAEs)
 
• Early discontinuations due to AEs
 
• Adjudicated cardiovascular and pancreatic AEs
 
• Thyroid neoplasms AEs
 
• AEs related to kidney failure, eGFR
 
• Systemic hypersensitivity AEs
 
• Local injection site reactions
 
• The change in systolic and diastolic blood pressure, heart rate, and lipids from baseline to 24 weeks
 
• Incidence and rate of hypoglycemic episodes
 
• Ketoacidosis, and initiation of rescue therapy for severe persistent hyperglycemia
 

**Objectives and Endpoints**

Objectives	Endpoints

Exploratory Exploratory efficacy objectives are to compare dulaglutide 1.5 mg and 0.75 mg to placebo at 24 weeks
	
 
• Proportion of patients meeting the composite endpoint of HbA1c <7.0%, no weight gain, and no documented symptomatic hypoglycemia
 
• Proportion of patients meeting the composite endpoint of HbA1c <7.0%, body weight loss >5%, and no documented symptomatic hypoglycemia
 

Abbreviations: AE = adverse event; eGFR = estimated glomerular filtration rate; FBG = fasting blood glucose; HbA1c = hemoglobin A1c; SGLT2 = sodium-glucose co-transporter 2; SMPG = self-monitored plasma glucose; T2D = type 2 diabetes.

## 5. A Priori Statistical Methods

### 5.1. Determination of Sample Size

With 120 completers per arm, the study will have 90% power for demonstrating superiority of either dulaglutide 1.5 mg or 0.75 mg versus placebo in change from baseline in mean hemoglobin A1c (HbA1c) at 24 weeks, assuming a standard deviation (SD) of 1.2%, a difference between dulaglutide and placebo of 0.55%, and a 2-sided significance level of 0.025. Assuming that the dropout rate is 15% for the entire study period, the study will need to enroll at least approximately 142 patients in each arm for a total of 426 patients enrolled. Assuming a screen fail rate of 40%, a total of approximately 710 patients will be screened to meet these enrollment number requirements.

### 5.2. General Considerations

Statistical analysis of this study will be the responsibility of Eli Lilly and Company (Lilly) or its designee. Any change to the data analysis methods described in the protocol will require an amendment ONLY if it changes a principal feature of the protocol. Any other change to the data analysis methods described in the protocol, and the justification for making the change, will be described in the SAP or the clinical study report (CSR). Additional exploratory analyses of the data will be conducted as deemed appropriate.

The primary analysis population will be the intent-to-treat (ITT) population, defined as all patients randomized who have received at least 1 dose. This is also the safety population. A select number of measurements (HbA1c, percent to goal in HbA1c, fasting blood glucose [FBG], and body weight) will also be evaluated in the per-protocol (PP) population and completer population. The PP population will include patients without important protocol deviations, took no concomitant medications that would confound the interpretation of results (such as systemic steroids or non-study glucose-lowering agents used >14 days), and have an HbA1c measurement at the primary visit endpoint ([Table GBGE.5.1](#)). The completer population will be based on patients who completed the treatment period ([Table GBGE.5.1](#)).

There will be 2 primary estimands to compare the placebo and the dulaglutide arms in terms of the primary measure of HbA1c change from baseline to 24 weeks. One primary estimand will be an efficacy estimand which will not use post-rescue data; the other primary estimand, requested by the US Food and Drug Administration (FDA), will be an ITT estimand (treatment regimen estimand) which will use post-rescue data. The efficacy estimand compares the benefit of the initially randomized treatments assuming all patients remained in the study and did not take additional or alternative antihyperglycemic medication. The estimate of mean change from baseline to endpoint reflects what would have been observed if patients stayed on their initially randomized treatments. The treatment-regimen estimand compares the benefit of treatment regimens as they are actually taken. The estimate of mean change from baseline to endpoint reflects what was actually observed regardless of use of any additional or alternative antihyperglycemic agents. Both estimands will use the same primary analysis model, and each will be tested at the full significance level of 0.05.

Analyses of the key secondary efficacy outcomes (percent to goal in HbA1c, FBG, body weight) and hypoglycemia will be performed on the full dataset with and without censoring data collected after rescue medication for any reason.

Unless otherwise noted, all tests of treatment effects will be conducted at a 2-sided alpha level of 0.05, and confidence intervals (CIs) will be calculated at 95%, 2-sided. All tests of interactions between treatment groups and other factors will be conducted at a 2-sided alpha level of 0.10.

The baseline will be Visit 5, except for HbA1c. Patients who do not need stabilization will have blood drawn for baseline HbA1c at Visit 2, and those who need stabilization at Visit 4. For all variables except HbA1c, if baseline data are missing, the last nonmissing measurement taken prior to Visit 5 will be used for the baseline measurement. For HbA1c, if baseline data are missing, the imputation will be conducted only if an additional value between Visit 2 and randomization (patients not needing stabilization) or Visit 4 and randomization (patients needing stabilization) is collected. The endpoint for the primary analysis is defined as the change from baseline in HbA1c at 24 weeks (Visit 11). Key secondary endpoints are percent to goal in HbA1c (<7.0%) at 24 weeks and change from baseline in FBG (central laboratory) and body weight at 24 weeks.

Two analysis models will be used for the primary and key secondary continuous efficacy measures. The primary analysis will be mixed-model repeated measure (MMRM) analysis using restricted maximum likelihood (REML). An unstructured covariance structure will be used to model the within-patient errors. If this model fails to converge, the following covariance structures will be tested in order:

- Toeplitz with heterogeneity
- autoregressive with heterogeneity, by visit
- compound symmetry with heterogeneous variances by visit,
- Toeplitz
- autoregressive
- compound symmetry without heterogeneous variances, by visit

The first covariance structure that converges will be used.

The secondary analysis for the primary and key secondary continuous endpoints will be analysis of covariance (ANCOVA). Missing endpoints will be imputed with the last (postbaseline) observation carried forward (LOCF). The percentage of patients achieving the target HbA1c of <7.0% at 24 weeks will be analyzed using a longitudinal logistic regression with repeated measurements.

A graphical testing approach will be used to strongly control for type 1 error to test for superiority of each of the dulaglutide doses versus placebo at 24 weeks for the following

measures: (1) change from baseline in HbA1c, (2) change from baseline in FBG (central laboratory), (3) percent achieving HbA1c <7.0%, and (4) change from baseline in body weight.

[figure not shown]
For continuous measures, summary statistics will include sample size, mean, SD, median, minimum, and maximum for both the actual and change from baseline measurements. Least-squares mean (LS mean) and standard errors derived from the model will also be displayed for the change from baseline measurements. Treatment comparisons will be displayed showing the treatment difference LS mean and the 95% CIs for the treatment differences (dulaglutide – placebo), along with the p-values for the treatment comparisons.

For categorical measures, summary statistics will include sample size, frequency, and percentages. Fisher's exact test will be used for treatment comparisons, unless 80% of cells have an expected value of at least 5, in which case the chi-square test will be used.

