**Table GBGE.5.1. Analysis Populations**

Population	Definition
All Entered	All patients who signed informed consent forms (ICF)
All Randomized	All patients who were randomized to a treatment arm
Non-randomized	All patients who entered, but not randomized, to a treatment arm
Intent-to-treat (ITT)	All randomized patients who have taken at least one dose of the study medication
Per-protocol (PP)	All patients in ITT and who also meet the following criteria: 
 
• Have no important protocol deviations (Section 5.7)
 
• Completed the treatment phase (24 week [Visit 11]) for primary end point (ie, did not discontinue from the study early)
 
• Are at least 75% compliant with study drug for at least 75% of the visits
 

Completer Population	The completers population will be defined as those who: 
 
• Completed the treatment period (ie, did not discontinue early from the study)
 

The complete list of protocol deviations leading to exclusion from the PP population is provided in Section 5.7.

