## 5.5. Patient Disposition

A listing of patient discontinuation will be presented for all randomized patients. Frequency counts and percentages of all patients entered, randomized/enrolled, completing and discontinuing from the study and study treatment will be presented for all treatment groups. A summary of discontinuations will also be presented by visit. The overall percent discontinued comparisons among the treatments will be performed using a Chi-square test or Fisher's exact test.

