## 5.7. Protocol Deviations

Important protocol deviations will be listed for all randomized patients. The rationale for choosing the important protocol deviations was based on their potential to impact the primary analysis. The following protocol deviations will be considered important and patients with these protocol deviations will be excluded from the PP population:

- Patients violating the following Inclusion/Exclusion criteria:

- Have HbA1c <7.0% or >9.5% at study entry (Visit 1) or at Visit 2 for patients without stabilization; HbA1c <7.0% or >9.5% at study entry (Visit 1) or at Visit 4 for patients with stabilization;
- Patients with Type 1 diabetes
- Have any hematologic condition that may interfere with HbA1c measurement (for example, hemolytic anemia, sickle-cell disease)
- Use of weight loss drugs within 3 months prior to study entry or use of systemic glucocorticoids 1 month prior to study entry, or use of these medications between study entry and Visit 5;
- Use of ANY other oral antihyperglycemic medications (OAMs) (other than sodium-glucose cotransporter 2 [SGLT2] inhibitors and metformin), GLP-1 receptor agonist (RA), pramlintide or insulin 3 months prior to study entry, or between study entry and Visit 5; or initiation of metformin between study entry and Visit 5; short-term use of insulin for acute care ( $\leq 14$  days) during the 3-month period prior to entry is not protocol deviation;
- Missing HbA1c at baseline (Visit 5) or at 24 weeks (Visit 11)
- Patients who do not have an overall compliance with study drug at least 75% for at least 75% of the visits during the study
- Patients who took medications that were prohibited per protocol for >14 days (cumulative) after randomization (Visit 5-Visit 11), including:
  - Excluded antihyperglycemia medications; including insulin use for acute care; Note: use of rescue therapy medications is not considered protocol deviation;
  - Other protocol-prohibited medications (systemic glucocorticoids or weight loss medications);
- Informed consent was never obtained
- Patients who are randomized but the informed consent data is missing.

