## 5.9. Study Drug Compliance

Study drug compliance for each visit is defined as taking at least 75% of the scheduled injections of the study drug for the period preceding that visit. Overall treatment compliance for each patient is defined as taking at least 75% of the injectable study drug for at least 75% of the visits, that is, the overall compliance percentage is at least 75% for this patient. The overall compliance in percentage for each patient will be calculated by taking the number of visits the patient was compliant divided by the total number of visits with non-missing compliance data for this patient \*100. Study drug compliance will be listed and summarized using ITT population. The compliance will be summarized and presented in descriptive statistics that include the sample size (n), mean, SD, median, min, and max. The frequency and percent of patients who are compliant will be compared between the treatment groups using Chi-square test or Fisher's exact test at each visit and overall.

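### The efficacy estimand targets patients who stay on randomized treatment but excludes only post-rescue values, so any values collected after study drug is stopped without rescue would count as on-drug

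*SAP*

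**What the plan says.** Section 5.2 describes the efficacy estimand in three steps.

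- Data rule: "One primary estimand will be an efficacy estimand which will not use post-rescue data".
- Condition: the treatments are compared "assuming all patients remained in the study and did not take additional or alternative antihyperglycemic medication".
- Target: "The estimate of mean change from baseline to endpoint reflects what would have been observed if patients stayed on their initially randomized treatments".

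Its counterpart, the treatment-regimen estimand, uses the same model and adds the post-rescue data, so rescue alone separates the two datasets. For the key secondary outcomes and hypoglycemia, Section 5.2 plans analyses "with and without censoring data collected after rescue medication for any reason". Section 5.12.3 repeats the rescue-only rule for the HbA1c target. The primary mixed model for repeated measures (MMRM) in Section 5.11 has no term for being on or off drug.

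In Section 5.11.1 the pMI acts on missing and post-rescue data, and the tipping-point analysis shifts only imputed values.

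On stopping drug as an event, Section 5.5 says that counts of patients "completing and discontinuing from the study and study treatment will be presented for all treatment groups", and Section 5.10 ends exposure when treatment is discontinued. Table GBGE.5.1, by contrast, glosses completing treatment as not leaving the study early, and Section 5.15.1 speaks only of study discontinuation due to adverse events.

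**The concern.** Both estimands share one model, so the data rule is all that makes the first an efficacy analysis. The rule fits the condition: leaving the study produces missing data, and rescue data are excluded. It does not fit the target sentence, because a patient can leave randomized treatment without taking rescue and without leaving the study. Any later value from such a patient is observed, unrescued and retained.

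At stake is the meaning of one of the two primary analyses, for which Section 5.3 also runs the graphical testing scheme separately. With off-drug values included, the estimate would no longer answer the question set for it, and the two MNAR-type analyses would not reveal this. For fasting blood glucose, the LOCF approach in Section 5.12.2 could also carry an off-drug value forward to week 24. An unstated rule leaves the choice to be made at programming.

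**Working it through.** **1. The plan's own figure.** Inputs from Section 5.1: difference 0.55, SD 1.2, two-sided alpha 0.025, power 90%, dropout 15%.

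- n per arm = 2 × (2.2414 + 1.2816)² × 1.2² / 0.55² = 118.2, so 119 (SAP: 120).
- Power at 120 per arm: 0.905 by the normal approximation, 0.901 by noncentral t (SAP: 90%).
- Enrolment: 120 / 0.85 = 141.2, so 142 per arm; 142 × 3 = 426 (SAP: 142 and 426).

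The sample size reproduces and is not in dispute.

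**2. Each departure from randomized treatment against the data rule.**

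| Event | Breaks the target? | Efficacy dataset | pMI / tipping point |
|---|---|---|---|
| Leaves study | yes | later values missing | covered |
| Takes rescue | yes | later values excluded | pMI names post-rescue data |
| Stops drug, no new agent, stays, values collected | yes | values kept | not covered: neither missing, imputed nor post-rescue |

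Only the third row is open.

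**3. Does that row contain anyone?** Sections 5.5 and 5.10 treat stopping drug as an event of its own. The gloss in Table GBGE.5.1 and the wording of Section 5.15.1 lean towards drug stop meaning study exit. The SAP does not resolve this. Whether values are collected after drug stop is a protocol matter.

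**4. Size, for scale only.** Let s be the share of a dulaglutide arm's week-24 values that is off drug without rescue, and f the fraction of benefit lost. Both are assumed; the SAP gives neither. Stopping placebo is assumed not to change the placebo mean.

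Reduction in the difference = 0.55 × s × f. Planned SE = 1.2 × √(2/120) = 0.155.

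| s | f | Reduction | Difference | Reduction / SE |
|---|---|---|---|---|
| 0 | any | 0 | 0.55 | 0 |
| 1% | 0.5 | 0.00275 | 0.54725 | 0.018 |
| 1% | 1 | 0.0055 | 0.5445 | 0.036 |
| 5% | 0.5 | 0.01375 | 0.53625 | 0.089 |
| 5% | 1 | 0.0275 | 0.5225 | 0.178 |

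In the last row, power at 120 per arm would be 87.1% instead of 90.5%. The proposed rule would not simply restore that, because it also removes observations; no power gain is claimed.

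**The case against.** The strongest objection is that the problem exists only if patients are followed after stopping drug. That fact belongs to the protocol, and parts of the SAP suggest that they are not. This stands as a limit on the consequence: the effect may be nil. It does not dispose of the point, because deciding which collected values enter which estimand is the SAP's task, and Section 5.2 takes it on.

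It can also be said that the data rule matches the two-part condition and only the next, looser sentence reaches further. That is fair, and it narrows the gap to the one group in the table. But the looser sentence is where the SAP says what the estimate means.

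A reader might infer that the per-protocol and completer repeats of the MMRM catch these patients only in part. The per-protocol rule is "Are at least 75% compliant with study drug for at least 75% of the visits", and Section 5.9 computes overall compliance as compliant visits "divided by the total number of visits with non-missing compliance data for this patient". With six visits assumed after randomization, a patient off drug for the last interval scores 5/6 = 83.3% and passes. The SAP does not support the inference. It requires the gloss in Table GBGE.5.1 to override the plain requirement to have completed treatment, and it assumes visit and compliance patterns that are not given. If the plain wording governs, both repeats exclude these patients. If the gloss equates drug stop with study exit, the group is empty. So no claim is made about the cover these repeats give.

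**Conclusion.** The mismatch between target and data rule is real and visible within Section 5.2, but its effect is conditional on values being collected after drug stop from unrescued patients who stay in the study. If they are, the bias is expected to run towards no difference and is small at the assumed shares of 0 to 5%: at most 0.0275 on a planned 0.55. That size rests wholly on the assumed s and f; the formula is linear and can be rescaled.

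A reader might infer a threat to the superiority claim or to type I error. Neither follows, because diluting the dulaglutide effect is conservative for superiority. The treatment-regimen estimand, which is meant to use values as observed, is not affected. The point is worth correcting because it concerns a primary analysis and costs little, not because it endangers the trial's conclusion.

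**What to change.** In Section 5.2, define the efficacy-estimand dataset for HbA1c and the key secondary endpoints as excluding values after the earlier of first rescue or permanent discontinuation of study drug. The sponsor should fix the analysis window around the drug-stop date before unblinding. Treat the excluded values as missing, so that for HbA1c the pMI and tipping-point analyses in Section 5.11.1 cover them. Keep all values for the treatment-regimen estimand.

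If no values are collected after drug stop, this rule changes nothing, and one sentence in Section 5.2 stating the fact is enough.

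The cost is one paragraph and one censoring flag, built from the treatment end date that Section 5.10 already needs. The drawback is that slightly more data are handled under MAR in the efficacy analysis, with a small loss of precision.
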